Patients will be identified from mental health teams' caseloads and will be offered the intervention if they do not show substantial risk to self or others and this should be monitored as per routine clinical practice. The clinician delivering the intervention will not be the treating clinician of the patient.

Clinicians should meet patients six times over the six-month intervention period; about once per month.

The intervention should start with a sufficiently long first two meetings (about 60 minutes) in the first month to explore preferences, discuss options in detail and agree on the way forward. The following meetings should discuss progress and provide support as required. They should last at least 20 minutes. Further contacts of clinicians with patients, as needed via telephone, text messages, Skype or other electronic means, will be encouraged. Such contacts may also replace face-to-face contacts, but the initial meeting and at least one more meeting will be face-to-face. The location of these meetings can vary and depend on patient preference and local circumstances (including patients' homes, community places and offices of services).

b. Content of meetings

The meetings should focus on the patient's motivation to expand social networks, their preferences for how to do this, local options for doing this and plans for how to achieve it in practice. This may include temporary support through the intervention (e.g. reminders, initial accompanying). The planned activities should be a way to expand social networks, e.g. leisure activities in groups rather than going to the cinema on their own. This will usually mean establishing new contacts, but could also be engaging in new joint activities with previous contacts (outside on-going friends and close family). The intervention will not address potential difficulties in already existing on-going relationships (e.g. with close family).

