Adherence to manual will be assessed through the use adherence checklist, routine documentation (recording document after each session), and audiotapes of patient professional meetings (as far as these can be collected).

Economic evaluation

We will assess costs related to delivery of the intervention based on the professionals involved and the number of sessions offered. We will also collect use of services in the experimental and control group by retrospective participant self-report using a relevantly modified version of the Client Services Receipt Inventory. We will use the EQ-5D-3L and ICECAP-A and evaluate their ease of administration and patterns of missing data in order to choose the final measure to use for cost-effectiveness analysis in the subsequent large trial.

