7 STATISTICS AND DATA ANALYSIS

Objective 1 and 2:

We will gain further experience of how the intervention is delivered in NHS settings and will carry out qualitative interviews with patients and clinicians. We will discuss with the steering group and the LEAP findings from qualitative material from audio-recordings of sessions, open ended sections of the fidelity instrument and clinician and patient interviews with the steering group in order to decide on whether any further modifications to the intervention or the training manual are required.

Objective 3:

In order to assess the feasibility of recruitment and randomisation procedures, the number of screened participants, eligible participants and of those who refused participation or were not approached will be recorded. The number of participants who withdraw from the study will also be recorded. Screening, recruitment and retention will be presented as rates with 95% confidence intervals. Descriptive statistics (mean (sd) for continuous variables and count (%) for nominal) will be reported for socio-demographic data and on social contacts, social activities, quality of life and symptoms scores. Changes in number of social contacts, time spent in social activities, quality of life and symptoms following the intervention will be reported as estimates with 95% confidence intervals. No efficacy related statistical tests will be conducted.

Objective 4:

We will estimate excess treatment costs more in detail through obtaining information from clinical records on the number of sessions offered and whether additional sessions need to be offered because of non-attendance. This will be analysed through descriptive statistics.

We will explore two different methods to calculate cost-effectiveness of the intervention using the EQ-5D-3L and the ICECAP-A. We will explore ease of administration of both instruments through interviews with patients and analyse frequency and type of missing data through descriptive statistics. The final decision on what instrument to be adopted will be made by the programme management group following discussion with the steering group and the lived experience advisory panel.

Objective 5:

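### Costing delivery from professionals and sessions offered does not measure clinician time, because four of the six meetings have only a minimum length and further contacts are not counted

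*Protocol*

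**What the plan says.** Objective 4 of the trial (Study summary) is to refine the methods for costing the intervention before the full trial. The protocol sets out the delivery costing in two places.

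- Section 6, Economic evaluation: "We will assess costs related to delivery of the intervention based on the professionals involved and the number of sessions offered".
- Section 7, Objective 4: excess treatment costs are to be estimated "through obtaining information from clinical records on the number of sessions offered and whether additional sessions need to be offered because of non-attendance".

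Section 6, Intervention, describes what is being costed. There are six meetings over six months. On length: "The intervention should start with a sufficiently long first two meetings (about 60 minutes) in the first month", and for the remaining meetings: "They should last at least 20 minutes". No maximum is given. On mode: "Further contacts of clinicians with patients, as needed via telephone, text messages, Skype or other electronic means, will be encouraged", and "Such contacts may also replace face-to-face contacts, but the initial meeting and at least one more meeting will be face-to-face". On place: "The location of these meetings can vary and depend on patient preference and local circumstances". On content: "This may include temporary support through the intervention (e.g. reminders, initial accompanying".

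Under Adherence to manual, Section 6 also plans a recording document after each session. It is named there as a source for adherence, not for costs.

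**The concern.** The costing passages name two inputs, who delivers and how many sessions are offered, plus repeat sessions after non-attendance. Neither mentions minutes, mode, between-session contact or time spent accompanying a patient. The intervention is deliberately flexible on all of these, so two patients with the same count can use quite different amounts of clinician time.

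A feasibility trial with a costing objective is the natural place to learn how much time delivery takes. Minutes not recorded during delivery cannot be reliably reconstructed later. Section 6.5 proposes carrying participants' data into the full trial if there are no major amendments, so a gap here could persist for these patients. Randomisation, sample size and the clinical estimates are unaffected.

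**Working it through.** The protocol states no cost or total of minutes, so there is no figure of its own to reproduce. The check is arithmetic on the planned meeting lengths.

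**Inputs from the protocol.** Six meetings; about 60 minutes for the first two (read as each of the two); at least 20 minutes for the other four; 32 intervention patients and 12 clinicians (Section 7.2).

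**Assumed.** Later meetings of 30, 40 or 60 minutes, all of which the text permits; between-session contacts of 10 minutes each.

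1. Single meetings: 60 / 20 = 3. This difference is scheduled, so applying planned lengths to the count recovers it.
2. Planned minimum per patient: 2 × 60 + 4 × 20 = 200 minutes. With planned lengths applied, everyone offered six sessions is assigned this figure.
3. Later meetings of length L: total = 120 + 4L.
   - L = 20: 200 minutes
   - L = 30: 240 minutes (+20%)
   - L = 40: 280 minutes (+40%)
   - L = 60: 360 minutes (+80%, or 360 / 200 = 1.8-fold)
4. Six offered, only the first two attended: 2 × 60 = 120 minutes delivered. The assigned 200 overstates this by 200 / 120 = 1.67. The error can therefore go either way.
5. Whole arm: 32 × 6 = 192 sessions. The same 192 correspond to 32 × 200 / 60 = 106.7 hours at the minimum, and to 128, 149.3 or 192 hours at L = 30, 40 or 60. Per clinician (divide by 12) this is 16 sessions and 8.9, 10.7, 12.4 or 16 hours.
6. Uncounted contacts: 3, 6 or 12 per patient at 10 minutes add 30, 60 or 120 minutes to 200. Their share of total contact time is 30 / 230 = 13%, 60 / 260 = 23% or 120 / 320 = 38%. The session count stays at six.
7. Mode: six meetings less the two that must be face-to-face leaves up to four that may be remote, again with the count unchanged.

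**The case against.** The strongest reply is that this is detail for an analysis plan or a data form. The protocol says costs are based on these inputs, not confined to them; it writes no unit cost and excludes no duration. That is fair as far as it goes. But the protocol names both the driver and, in Objective 4, its source, and nothing in it commits anyone to using minutes.

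A second reply is that the recording document may already hold mode and minutes. It may, since its fields are not shown. A reader might infer that these data will not be collected, and the documents do not support that. If the fields exist, only the link to costing is missing.

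Third, the planned audio-recordings show their own duration. Section 6 aims for three sessions per clinician and Section 2 for two, so 24 to 36 of 192 sessions. They depend on consent and are named for adherence, so they give a partial check rather than a costing source.

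Fourth, a reader might take three-fold as the size of the costing error. It is not: that gap is mostly scheduled, and the remaining spread rests on assumed lengths.

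Finally, a reader might infer that the statement in Section 6, Payment to participants, about little effect on working time is in doubt. These figures do not show that. Even 16 hours per clinician is 1.6% of an assumed 975 working hours (26 weeks of 37.5 hours); the minimum of 8.9 hours is 0.9%.

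**Conclusion.** The point holds as a low-severity improvement to how Objective 4 is met. Costing from professionals and sessions offered does not measure clinician time for this intervention. With planned lengths applied, the method assigns 200 minutes to every patient offered six sessions. The delivered session total could be 120 if only the first two are attended, or 240 to 360 if later meetings run 30 to 60 minutes, with between-session time on top. The range above 200 rests on assumed lengths and is at most 1.8-fold even when every later meeting is as long as the first. The documents do not show how large the spread will be in practice, which is the reason to record it.

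**What to change.** In the Economic evaluation paragraph of Section 6 and under Objective 4 in Section 7, keep sessions offered and non-attendance, and add one sentence to each:

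- Attendance, mode (face-to-face, telephone, video, text) and minutes will be taken from the recording document completed after each session, with these fields added if absent, and used to cost delivery by professional and mode.
- A simple total of between-session contact and accompanying time will be kept for each patient.
- Delivered sessions and minutes per patient will be reported descriptively.

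Non-attended sessions stay as a separate item, since a missed appointment can still use clinician time. Logging every text message or travel time can be optional.

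The cost is a little clinician recording time. At an assumed one minute per form, 192 forms take 192 minutes (3.2 hours) in total, or 192 / 12 = 16 minutes per clinician over six months. Between-session entries come on top: one entry per patient per month (assumed) is another 32 × 6 = 192 minutes, a further 16 minutes per clinician. These contacts have to be noted as they happen.

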6.1 Recruitment

Patients will be identified through screening community mental health teams' caseloads, primary care caseloads and through the data base of participants of the previous work packages who expressed an interest to take part in the intervention. At this stage, the minimum amount of information will be logged to ascertain eligibility: name, RIO or NHS number, inpatient status (to ascertain eligibility) and diagnosis. We will discuss with treating clinicians if patients are deemed to be socially isolated. Addresses will only be logged for patients eligible to the intervention, so that letters can be sent inviting them to take part.

6.1.1 Patient identification

Mental health professionals with different roles who fit the eligibility criteria will be asked to participate. They will be approached by email, letter, phone or in person.

Patients on community team caseloads will be screened for eligibility by clinical teams. Clinicians will contact patients (by phone or face-to-face) and if patients verbally agree to meet a researcher, they will be invited to the baseline interviews with researchers. The research team will not contact patients unless they have received permission from clinicians or participants from the previous part of the project to do so. Once patients verbally agree to meet a researcher, the clinicians will share permission and patients' contacts with researchers through encrypted email networks, phone or face-to-face meetings. The researchers will then contact patients face to face or via phone, offering to send participant information sheets via post or directly providing them if the meeting is face to face. The

baseline interview could follow during the same session or patients will be allowed one week to think about their participation.

The eligibility will be then confirmed during the baseline interviews by the research team with reference to the criterion of "5 or less score on the MANSA "

If patients meet all the inclusion criteria, they will be invited to participate in the intervention and in the follow-up quantitative and qualitative interviews. The interviews will take place within NHS facilities, quiet rooms at the participating Universities or at patients' home based on patients' preferences.

6.2 Consent

All patients who respond to study information with interest will be contacted and invited to attend a face-to-face meeting. Researchers will go through information sheets with interested individuals and time taken to answer any questions or concerns that are raised.

All participants will be asked to provide informed consent, by initialling, signing and dating an informed consent form before any data collection begins. If patients require some time to think about participation, they will have up to one week to do so, otherwise the baseline interview will be done on the same day. A written consent form will need to be signed by the participant and a member of the research team in order to proceed with study participation. The participant will keep one copy and the research team will keep the original which will be scanned and uploaded to the electronic medical records. Participants will also be given the option during the consent process to receive findings from the study, and permission will be sought to access medical records to retrieve clinical characteristics. Patients will also be asked if they consent to some of the sessions being audio-recorded, but this will be an optional criterion and they will still be able to participate if they refuse that their sessions are audio-recorded. Only patients who are fully eligible to the intervention will then be invited to participate in it.

Research team members will ensure each person's level of understanding during the recruitment and consent process, alongside discussion with patients' clinicians where necessary. Researchers will discuss the information sheet with patients and answer any questions they might have. If there are any doubts about the person's capacity to consent, this will need to be resolved before proceeding with study participation. If any doubts about their capacity emerge during the recruitment process, or capacity to consent appears to change during their participation in the study, their capacity to consent will be re-evaluated before continuing with study participation. For each intervention session any change in capacity to consent will be evaluated by experienced clinicians according to standard practice.

If patients decline to participate, or withdraw their participation, this decision will be respected and patients are not required to give a reason for declining or withdrawing their participation. This decision will not have any impact on the patient's treatment or rights, and this will be made clear to patients on the information sheet and by researchers during the consent process.

6.3 Study assessments

Socio-demographic and clinical characteristics will be collected from all patient participants. A modified form will be used to collect socio-demographic data from clinician participants. Qualitative data only will be collected through individual interviews. There will be baseline and follow up interviews to collect data on patients' social contacts and social activities, quality of life and symptoms.

6.4 Withdrawal criteria

During the consent process, researchers will ensure that participants (both patients and clinicians) are aware of their right to decline participation at any stage of the research and that withdrawing participation will not affect their treatment or rights. Participants will be able to ask that their data is eliminated before the end of February 2019.

For WP4, if patients withdraw from the intervention, then the research team will ask permission to contact them to take part in the post-intervention qualitative interview in order to capture valuable information regarding reasons for withdrawal, which might be associated with the intervention. This will be explained to patients during the consent process and on the information sheet, and patients' decisions to not be contacted for the post-intervention interview will be respected.

If a participant wishes to withdraw from the study, researchers will record date of withdrawal and reason(s) for withdrawal.

Clinicians delivering the intervention will monitor the capacity throughout the intervention duration. If a participant, who has given informed consent, loses capacity to consent during the study. The participant would be withdrawn from the study. Identifiable data or tissue already collected with consent would be retained and used in the study.

6.5 Future Study

If following this feasibility trial there will be no major amendments to the intervention or research procedures, we will propose to the independent Programme Steering Group that: a) we will continue recruitment for a full hypothesis testing randomised controlled trial; b) we will use participant data from the feasibility trial (WP4) in the subsequent full randomised controlled trial (Work Package 5).

If the independent Programme Steering Group will approve our proposals we will submit the protocol for the full randomised controlled trial to the ethics committee as a major amendment.

7 STATISTICS AND DATA ANALYSIS

Objective 1 and 2:

We will gain further experience of how the intervention is delivered in NHS settings and will carry out qualitative interviews with patients and clinicians. We will discuss with the steering group and the LEAP findings from qualitative material from audio-recordings of sessions, open ended sections of the fidelity instrument and clinician and patient interviews with the steering group in order to decide on whether any further modifications to the intervention or the training manual are required.

Objective 3:

In order to assess the feasibility of recruitment and randomisation procedures, the number of screened participants, eligible participants and of those who refused participation or were not approached will be recorded. The number of participants who withdraw from the study will also be recorded. Screening, recruitment and retention will be presented as rates with 95% confidence intervals. Descriptive statistics (mean (sd) for continuous variables and count (%) for nominal) will be reported for socio-demographic data and on social contacts, social activities, quality of life and symptoms scores. Changes in number of social contacts, time spent in social activities, quality of life and symptoms following the intervention will be reported as estimates with 95% confidence intervals. No efficacy related statistical tests will be conducted.

Objective 4:

We will estimate excess treatment costs more in detail through obtaining information from clinical records on the number of sessions offered and whether additional sessions need to be offered because of non-attendance. This will be analysed through descriptive statistics.

We will explore two different methods to calculate cost-effectiveness of the intervention using the EQ-5D-3L and the ICECAP-A. We will explore ease of administration of both instruments through interviews with patients and analyse frequency and type of missing data through descriptive statistics. The final decision on what instrument to be adopted will be made by the programme management group following discussion with the steering group and the lived experience advisory panel.

Objective 5:

We plan to have different professionals delivering the intervention during the feasibility trial (e.g. psychiatrists, nurses, occupational therapists, senior psychologists and psychology graduates). The final decision on which type of professionals will be chosen to deliver the intervention will be made by the programme management group following discussion with the steering group and the lived experience advisory group. The discussion will be based on data from the adherence checklist and from the interviews with patients and clinicians.

Objective 6:

The data collected using the adherence checklist will be triangulated with audio-recordings of sessions to test whether there is concordance and the less expensive method (i.e. adherence checklist) is appropriate to measure fidelity in the trial. The audio-recordings will be rated by independent evaluators in the research team according to the same domains as found in the adherence checklist. We will calculate correlation rates through correlation statistics and report to the steering group. A final decision will then be made on whether to amend the current adherence checklist or use alternative methods to assess fidelity in the trial.

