During the current study we will test the feasibility of the intervention, recruitment and randomisation procedures through involving clinicians (e.g. assistant psychologists, nurses, trainee psychiatrists etc.) and asking them to deliver the intervention in practice to a small number of patients. To help the refinement we will adopt a mixed method approach. A qualitative approach will enable an in-depth consideration of the views of patients and clinicians in order to specify how the intervention needs to be adapted for delivery in routine mental health services. This will include audio-recording of part of the intervention sessions (we will aim to audio record two sessions per each clinician) in order to identify how the guidelines and training provided to the clinicians will determine the content of the meeting in practice and help further refinement of the training. We will also carry out quantitative assessments in order to be able to describe the characteristics of the sample and explore whether the intervention has a potential for changing outcomes such as number of social contacts and social activities, quality of life and symptoms. We hope that this work package will also help to refine the methods of assessing the costs of the intervention including the resources required for training and gain further and more systematic practical experience with the intervention in the NHS in preparation for a full randomised controlled trial.

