Knowledge about the local context will be helped by a list of possible local options for low cost activities in the local area available to the patient that involve contacts with other people. This list will be provided by the research team. Clinicians will also be expected to and supported in obtaining a good knowledge about the options and encouraged to network in the given community to generate more options for relevant activities. Learning progress will be assessed during the training and in the subsequent supervision, provided by senior members of the research team, which will be organised flexibly in order to identify the ideal frequency. At the end of the case studies, clinicians who have delivered the intervention will receive an in-depth interview and will be encouraged to provide suggestions for further refinement of the intervention, of the training and of the supervision arrangements.

e. Further support of clinicians

Clinicians will receive updates on changes in options for activities from the local research team and from participating clinicians themselves through networking. They will also be supervised through regular phone calls (at least once a month or more if and as required) either locally or centrally from the study team in London.

Recording of the intervention sessions

For each clinician, we will aim to audio-record three interventions sessions (if the patients consent to this). They will be helpful to understand what are the topics and activities discussed during the intervention sessions and to identify ways to help motivation and commitment of patients to social activities in order to help specify training guidelines and obtain examples to be used for a training package.

Control group

Patients in the control group will be provided with comprehensive information about local options for social activities by the researcher. This group is intended to control for the provision of information and non-specific attention through a professional in addition to routine care. Also, the mere provision of information should be regarded as good practice independent of additional targeted interventions, so that patients in the control group should receive it too.

The usual treatment, including care-coordination, medication, and psychological therapies, will not be affected, neither in the intervention nor in the control group.

Follow-up quantitative interviews with a researcher

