7.1 Qualitative and Quantitative Data Analysis Plan

Quantitative data will be analysed using descriptive statistics. Data on patient statements on reasons for not participating and thoughts about outcome measures will be subjected to content analysis.

Audio recordings of intervention sessions and interviews with clinician and patients will be transcribed verbatim and analysed using content analysis techniques. The steps for inductive content analysis outlined by Elo and Kyngäs (2007) will be followed. After familiarisation, two researchers will independently analyse the data. Open coding will be conducted, making notes and headings in the text in order to describe the content. The process of grouping similar codes under themes will follow. The identified themes and subthemes will be then checked and refined in order to enhance conformability and reduce bias (Elo et al., 2014).

To optimise validity, we will (1) ensure attention is paid to negative cases and (2) conduct respondent validation by checking the analytic interpretation with patients/professionals. Inter-rater reliability in applying second level codes (or categories) will be calculated on 20% of the data. If captured, recordings will be transcribed verbatim and analysed as described above. If possible, data from interviews, recording documents and recorded first sessions will be triangulated as a further validation procedure.

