9.3 Data protection and patient confidentiality

All researchers and study staff must comply with the requirements of the Data Protection Act 1998 with regards to the collection, storage, processing and disclosure of personal information and will uphold the Act's core principles.

Personal information:

All participants will be assigned a participant ID number and this will be used for all data processing purposes. Participants' names and contact details will be retained (with their permission) to share research findings. As the project linked to this is funded for five years, it is envisaged that participants might want to know how their information and suggestions have helped to shape the service on offer.

Directly identifiable patient data (participants' names, contact details, socio-demographic data) and the list linking these data with participant ID number will be password-protected and stored on secure servers at participating research sites', which will only be accessible by the research programme (SCENE) team members on a need-to-know basis. All hard copies of data including socio-demographic forms, consent forms, patient receipts will be kept in lockable filing cabinets on NHS premises of participating sites, and only accessible to the research team members on a need-to-know basis.

Electronic data transfer from the PCTU to ELFT will be carried out securely in accordance with PCTU processes. Lists linking participant names to participant ID numbers will remain with local sites.

Audio recordings

The interviews and some intervention sessions (initial two sessions and at least one follow-up session) will be audio-recorded with participants' permission. Audio recordings will be stored on secure servers in participating Trusts, with access restricted to appropriate members of the research team. Audio recordings from participating sites will be transferred to the host site using encrypted USB sticks or via an encrypted connection and then transcribed using a NHS-approved professional transcription company. The audio recordings will be destroyed immediately after transcription and analysis. We have the resources to conduct this additional follow-up session and analyse further data in a timely manner before the end of the study. Once transcribed, all identifiable information will be omitted or replaced with pseudonymised labels.

Record retention and archiving

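### Objective 6 asks whether the adherence checklist is concordant with rated recordings but names only correlation, which in its ordinary form would not show a systematic offset

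*Protocol*

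**What the plan says.** Section 7, Objective 6, compares the adherence checklist with the session recordings "to test whether there is concordance and the less expensive method (i.e. adherence checklist) is appropriate to measure fidelity in the trial". The reference standard is described as follows: "The audio-recordings will be rated by independent evaluators in the research team according to the same domains as found in the adherence checklist". The analysis is one sentence: "We will calculate correlation rates through correlation statistics and report to the steering group". The decision follows: "A final decision will then be made on whether to amend the current adherence checklist or use alternative methods to assess fidelity in the trial".

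No type of correlation, agreement measure or threshold is given. Section 7.1 adds only a general rule: "Quantitative data will be analysed using descriptive statistics". The inter-rater reliability in Section 7.1 concerns the coding of qualitative material, not the checklist against the recordings.

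The number of recordings is stated in more than one way. Section 2 says "we will aim to audio record two sessions per each clinician". Section 6, under the recording of intervention sessions, says "For each clinician, we will aim to audio-record three interventions sessions", subject to patient consent. Section 9.3 speaks of the "initial two sessions and at least one follow-up session) will be audio-recorded", without saying whether this is per clinician or per patient. Section 7.2 plans 12 clinicians.

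**The concern.** Whether one method can stand in for another on the same domains depends on whether the two give the same score for the same session. A correlation answers a different question: whether sessions that score high on one method also score high on the other. A checklist that is wrong in level by a constant amount passes that test as well as an accurate one.

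Testing methods for assessing adherence is one of the six specific objectives, and the choice of fidelity measure for the full trial follows from this comparison. If the level is wrong and nobody notices, fidelity in the full trial is misstated by the same amount. Objective 5 also draws on checklist data when choosing which professionals will deliver the intervention. A constant offset would cancel in that comparison, but one that differed between professions would not.

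**Working it through.** The protocol gives no figure for Objective 6, so there is none to reproduce. The check is of the property itself. The correlations and offsets below are assumptions chosen for illustration.

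**1. Effect of a constant offset.** Let both ratings have the same SD, let their correlation be r, and let the checklist lie d SD away from the recording on average. The correlation stays r whatever d is. Lin's concordance coefficient is CCC = 2r/(2 + d²). The absolute-agreement ICC, r/(1 + d²/2), takes the same value. The sign of d does not matter, so over-rating and under-rating count alike.

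| Correlation r | d = 0 | d = 0.5 | d = 1 | d = 2 |
|---|---|---|---|---|
| 1.00 | 1.00 | 0.89 | 0.67 | 0.33 |
| 0.90 | 0.90 | 0.80 | 0.60 | 0.30 |
| 0.80 | 0.80 | 0.71 | 0.53 | 0.27 |

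The cells are CCC. For example, 2 × 1.00/(2 + 1) = 0.67 and 2 × 0.80/(2 + 1) = 0.53. Along each row the correlation does not move.

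**2. A concrete case.** Recordings are rated 1, 2, 3 and 4 equally often (variance 1.25), and the checklist is always one point higher. Then r = 1.00, exact agreement is 0%, and CCC = 2 × 1.25/(1.25 + 1.25 + 1²) = 0.71.

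**3. Number of pairs.** Section 2 gives 12 × 2 = 24 recordings and Section 6 gives 12 × 3 = 36. Both are upper limits, because patients may decline recording. The Fisher-z 95% interval is tanh(atanh r ± 1.96/√(n − 3)), ignoring clustering by clinician.

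| r | n = 24 | n = 36 |
|---|---|---|
| 0.70 | 0.41 to 0.86 | 0.48 to 0.84 |
| 0.80 | 0.59 to 0.91 | 0.64 to 0.89 |

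Precision is limited with either target, and the choice between them changes it.

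**4. Would the mean difference show the offset at this size?** With equal SDs, the SD of the difference is √(2(1 − r)). At r = 0.80 this is √0.40 = 0.63 SD. The half-width of the 95% interval is then 1.96 × 0.632/√24 = 0.25 SD with 24 pairs, and 1.96 × 0.632/√36 = 0.21 SD with 36. At the extreme, where all recordings of one clinician carry the same difference, only 12 independent values remain, and the half-width is 2.201 × 0.632/√12 = 0.40 SD (t with 11 degrees of freedom). A 1 SD offset would be clearly visible in every case.

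**The case against.** Four points can be made for the plan as written.

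- **The term is generic.** An absolute-agreement ICC is itself a correlation statistic, and a statistical analysis plan that was not available for this review might name it. This stands. It would be too strong to say that the protocol fixes a method that cannot show agreement. The fair statement is that its wording permits a coefficient blind to offset and does not point to one that is not.
- **No acceptance rule is tied to the correlation.** A reader might infer that a biased checklist would be accepted. The protocol does not say so: results go to the steering group and a decision follows. Ordinary descriptive means by source could reveal a gross offset, although Objective 6 does not promise that comparison.
- **Uniform over-rating is not documented.** A reader might assume that clinicians rate themselves generously. The protocol does not say who completes the checklist, what its item scale is, or which way it might err. An offset need not be constant either. On an assumed four-point scale with recordings spread evenly over 1 to 4, over-rating by one point capped at 4 lowers r to 0.94, and by two points to 0.77. The correlation then reacts, though only slightly in the first case.
- **It is a process measure in a feasibility study.** The ratings are collected either way, and agreement could be computed later. This limits the severity.

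On the recording target, a reader might take Section 9.3 to mean three recordings for each of the 32 intervention patients, or 32 × 3 = 96. That section states no unit, and it can equally be read as the three per clinician of Section 6. The clear conflict is two against three.

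What remains is that the stated aim is concordance, the stated statistic does not ensure it is examined, and no other part of the protocol closes the gap.

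**Conclusion.** The point holds in this form: Objective 6 poses a question of agreement and names only correlation. If that means Pearson or Spearman, a constant offset in either direction would leave the planned statistic unchanged. That blindness is a mathematical property and rests on no assumption about the data. The sizes quoted, such as a concordance coefficient of 0.67 or 0.53 at a 1 SD offset, assume equal SDs and illustrative values of r. They are not predictions about this checklist.

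The conflict between two and three recordings per clinician is real but secondary, since the argument about the statistic does not depend on it. The matter should be fixed, but it is not critical: it touches no allocation, eligibility, safety or outcome estimate.

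**What to change.** In Section 7, Objective 6, replace the sentence on correlation with wording such as:

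*For each recorded session, agreement between the checklist and the evaluators' rating will be summarised by the absolute-agreement intraclass correlation (or Lin's concordance coefficient) for total scores, and by kappa or percent agreement for categorical items. The mean checklist-minus-recording difference will be reported with a 95% confidence interval that allows for clustering of sessions within clinician.*

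With 12 clinicians, a simple way to obtain that interval is to average the differences within each clinician and use a t interval with 12 − 1 = 11 degrees of freedom. A correlation may be kept as a supplement.

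State one recording target in Sections 2 and 6, and say in Section 9.3 whether its sessions are counted per clinician or per patient.

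The cost is protocol wording only if the number actually intended is simply written down. The same ratings on the same domains are analysed, and the choice of agreement statistic requires no further data.
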